6.4. Safety Analysis

All safety analyses will be summarized by treatment based on the Safety Set. Safety will be assessed by clinical review of all relevant parameters, including SAEs, AESIs, AEs leading to withdrawal, vital sign measurements, and physical examination findings.

6.4.1. Unsolicited Adverse Events

An AE is defined as any untoward medical occurrence associated with the use of a drug in humans whether it is considered drug related or not. SAEs, AESIs (defined in Protocol Table 4), and AEs leading to discontinuation of study participation will be collected throughout the study. All AEs started after the injection will be reported in summary tables.

Unsolicited AEs will be coded by SOC and PT according to MedDRA dictionary.

All summary tables for unsolicited AEs will be presented by SOC and PT for AEs with counts of participants included. Given study duration is approximately 2 weeks, the unsolicited AEs will be summarized throughout the study.

When summarizing the number and percentage of participants with an event, participants with multiple occurrences of the same AE or a continuing AE within SOC or PT group will be counted once. Separate listings for corresponding AE tables will also be provided.

In addition, adverse events based on CDC wording cased definition of pericarditis, myocarditis, and myopericarditis occurring after receipt of study vaccines (defined in Protocol Appendix 4) will be listed if data is available.

The number of events and number of participants with occurrences of selected AEs of clinical interests identified by SMQ throughout the study will be summarized for narrow scope, narrow and broad scope, separately.

6.4.1.1.AEs by System Organ Class and Preferred Term

The following summary tables of AEs throughout the study will be provided by MedDRA SOC and PT using frequency counts and percentages:

- All unsolicited AEs leading to discontinuation from participation in the study,
- All unsolicited AESIs.

6.4.1.2.Serious Adverse Events

The summary table of serious AEs throughout the study will be provided by SOC and PT using frequency counts and percentages.

Death events will be provided in a separate listing.

6.4.2. Vital Signs

Vital sign measurements, including systolic and diastolic blood pressures, heart rate, respiratory rate, and body temperature, will be presented in a data listing. The values meeting the toxicity grading criteria (DHHS 2007) will be flagged in the data listing.

6.5. Planned Analysis

The final analysis of all endpoints will be performed after participants have completed all planned study procedures. Results of the analysis will be presented in a final clinical CSR, including individual listings.

7. Changes from Planned Analyses in Protocol

Not applicable.

8. References

Guidance for Industry: Toxicity Grading Scale for Healthy Adult and Adolescent
Volunteers Enrolled in Preventive Vaccine Clinical Trials. U. S. Department of Health and
Human Services (DHHS). Food and Drug Administration. Center for Biologics Evaluation
and Research. September 2007.

9. List of Appendices

9.1. Appendix 1: Standards for Variable Display in TFLs

Continuous Variables: The precision for continuous variables will be based on the precision of the data itself. The mean and median will be presented to one more significant figure than the original results; the SD will be presented to two more significant figures than the original results; the minimum and maximum will be presented to the same precision as the original results.

Categorical Variables: Percentages will be presented to 1 decimal place. If the count is 0, the percentage will not be displayed. If the count equals the denominator, the percentage will be displayed as 100.

9.2.Appendix 2: Analysis Visit Windows

Analysis will be summarized using the following analysis visit window for post injection assessments:

Step 1: If the assessments are collected at a scheduled visit, the collected data will be mapped to the nominal scheduled visit.

Step 2: If the assessments are collected at an unscheduled visit, the collected data will be mapped using the analysis visit windows described in [Table 1](#) below.

If a participant has multiple assessments for the same analysis visit, the following rule will be used:

- If multiple assessments occur for both scheduled visit and unscheduled visit, the assessment collected at scheduled visit will be used.
- If multiple assessments occur for an analysis visit, the assessment closest to the target study day will be used.
- If there are 2 or more assessments with equal distance to the target study day, the last assessment will be used.

Table 1 Visit Window

Visit	Target Study Day	Visit Window in Study Day
Immunogenicity		
Day 1	1 (Date of the Injection)	1, Preinjection
Day 15	15	[12, 22]
Vital Signs		
Day 1	1 (Date of the Injection)	1, Preinjection
Day 1	1 (Date of the Injection)	1, Postinjection
Day 15	15	[12, 22]

9.3. Appendix 3: Schedule of Activities

Refer to Table 2: Schedule of Activities (SoA) in the protocol.

9.4. Appendix 4: Imputation Rules for Missing Dates of Prior/Concomitant Medications, Non-Study Vaccinations

Imputation rules for missing or partial start/stop dates of medication are defined below:

1. Missing or partial medication start date:
 - If only Day is missing, use the first day of the month, unless:
 - The medication end date is on/after the date of injection or is missing/partial AND the start month and year of the medication coincide with the start month and year of the injection AND the medication is not known to be taken prior to study administration (e.g. answer to the question of “Was the medication taken prior to study administration?” in CRF is not Yes). In this case, use the date of injection.
 - If Day and Month are both missing, use the first day of the year, unless:
 - The medication end date is on/after the date of injection or is missing/partial AND the start year of the medication coincide with the start year of the injection AND the medication is not known to be taken prior to study administration (e.g. answer to the question of “Was the medication taken prior to study administration?” in CRF is not Yes). In this case, use the date of injection.
 - If Day, Month, and Year are all missing, the date will not be imputed, but the medication will be treated as though it began prior to the injection for purposes of determining if status as prior or concomitant. However, if the medication is known to be not taken prior to study administration (e.g. answer to the question of “Was the medication taken prior to study administration?” in CRF is No), the medication will be treated as though it began after the injection for purposes of determining status as prior or concomitant.
 - 2. Missing or partial medication stop date:
 - a. If only Day is missing, use the earliest date of (last day of the month, study completion, discontinuation from the study, or death).

- b. If Day and Month are both missing, use the earliest date of (last day of the year, study completion, discontinuation from the study, or death).
- c. If Day, Month, and Year are all missing, the date will not be imputed, but the medication will be flagged as a continuing medication.

In summary, the prior, concomitant categorization of medications is described in the table below. Non-study vaccinations will be considered as prior if start date is before IMP.

Table 2 Prior, Concomitant, and Post Categorization of Medications

Medication Start Date	Medication Stop Date	
	< Injection Date of IMP	\geq Injection Date [2]
< Injection date of IMP [1]	P	P, C
\geq Injection date	-	C

C: Concomitant; P: Prior

[1] includes medications with completely missing start date

[2] includes medications with completely missing end date

Note: study duration is approximately 2 weeks. All medication taken on or after the dose date of study vaccine are considered concomitant medication.

9.5. Appendix 5: Imputation Rules for Missing Dates of AEs

Imputation rules for missing or partial start dates and stop dates of AEs are defined below:

1. Missing or partial start date:
 - If only Day is missing, use the first day of the month, unless:
 - The AE end date is on/after the date of injection or is missing/partial AND the start month and year of the AE coincide with the start month and year of the injection. In this case, use the date and time of injection, even if AE time was collected.
 - If Day and Month are both missing, the date will not be imputed, unless:
 - The AE end date is on/after the date of injection or is missing/partial AND the start year of the AE coincides with the start year of the injection. In this case, use the date and time of injection, when time is available.
 - If Day, Month, and Year are all missing, the date will not be imputed. However, if the AE end date is prior to the date of injection, then the AE will be considered a pre-treatment AE. Otherwise, the AE will be considered treatment-emergent.
2. Missing or partial end dates will not be imputed.

9.6.Appendix 6: Severity Grading of Vital Sign Abnormalities

Table 3 Vital Sign Abnormalities

Vital Signs*	Mild (Grade 1)	Moderate (Grade 2)	Severe (Grade 3)	Potentially Life Threatening (Grade 4)
Fever (°C)** (°F)**	38.0 – 38.4 100.4 – 101.1	38.5 – 38.9 101.2 – 102.0	39.0 – 40 102.1 – 104	> 40 > 104
Tachycardia - beats per minute	101 – 115	116 – 130	> 130	ER visit or hospitalization for arrhythmia
Bradycardia - beats per minute***	50 – 54	45 – 49	< 45	ER visit or hospitalization for arrhythmia
Hypertension (systolic) - mm Hg	141 – 150	151 – 155	> 155	ER visit or hospitalization for malignant hypertension
Hypertension (diastolic) - mm Hg	91 – 95	96 – 100	> 100	ER visit or hospitalization for malignant hypertension
Hypotension (systolic) – mm Hg	85 – 89	80 – 84	< 80	ER visit or hospitalization for hypotensive shock
Respiratory Rate – breaths per minute	17 – 20	21 – 25	> 25	Intubation

* Participant should be at rest for all vital sign measurements.

** Oral temperature; no recent hot or cold beverages or smoking.

*** When resting heart rate is between 60 – 100 beats per minute. Use clinical judgement when characterizing bradycardia among some healthy participant populations, for example, conditioned athletes.

For analysis purpose, the grades will be calculated using the numerical portion only.

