8.3.2. Time Period and Frequency for Collecting of Safety Information

All SAEs will be collected from the signing of the ICF until EoS at the timepoints specified in the SoA ([Section 1.3](#)). All SAEs will be recorded and reported to the Sponsor or designee immediately and under no circumstance should this exceed 24 hours, as indicated in [Section 8.3.7](#). The Investigator will submit any updated SAE data to the Sponsor within 24 hours of it being available.

All AEs leading to discontinuation will be collected from the signing of the ICF until the EoS at the timepoints specified in the SoA ([Section 1.3](#)).

All AESIs will be collected from the signing of the ICF until EoS at the timepoints specified in the SoA ([Section 1.3](#)).

Investigators are not obligated to actively seek information on AEs or SAEs after conclusion of the study participation. However, if the Investigator learns of any SAE, including a death, at any time after a participant has been discharged from the study, and the Investigator considers the event to be reasonably related to the study intervention or study participation, the Investigator must promptly notify the Sponsor.

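### The AE year-only start-date rule can place onset at injection even when the recorded end month is already over

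*SAP*

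**What the plan says.** SAP Appendix 5 has three branches for incomplete AE start dates.

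- **Day missing.** The first of the month is used. The injection date and time replace it when the end date is on or after injection, or is missing or partial, and "the start month and year of the AE coincide with the start month and year of the injection".
- **Day and month missing.** "If Day and Month are both missing, the date will not be imputed, unless" the end date is on or after injection or "is missing/partial AND the start year of the AE coincides with the start year of the injection". The instruction is then: "In this case, use the date and time of injection, when time is available".
- **Whole date missing.** Nothing is imputed, but "if the AE end date is prior to the date of injection, then the AE will be considered a pre-treatment AE"; otherwise it is treatment-emergent.

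For end dates the appendix says: "Missing or partial end dates will not be imputed".

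SAP 6.4.1 puts into the summary tables those AEs that started after the injection. Protocol 8.3.2 opens collection before dosing: "All SAEs will be collected from the signing of the ICF until EoS". It gives the same period for AESIs and for AEs leading to discontinuation.

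SAP Appendix 4 uses the same construction for medications: "The medication end date is on/after the date of injection or is missing/partial AND the start year of the medication coincide" with the injection year. It adds one further condition, that the drug is not known from the CRF to have been taken before study administration.

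**The concern.** Imputing onset to the injection is a sensible conservative default when the timing relative to injection is unknown. The year-only branch goes further. It treats every partial end date as uninformative, including one whose recorded month has ended before the injection. The result is an onset later than the event's own end, and no later step repairs the order because partial end dates are left as collected.

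The consequence falls on the secondary safety endpoint. An SAE, AESI or AE leading to withdrawal that preceded injection could be carried into a by-arm post-injection table, with an impossible date order in the listing. The plan randomizes about 200 participants 1:1, so one misplaced event would move an arm of about 100 from 0% to 1%.

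**Working it through.** The documents give no figure to reproduce. The check applies the rule literally to test dates and then counts calendar days.

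**Logic.** Let A = complete end date on or after injection, B = end date missing or partial, and C = start year equals injection year. The sentence can be read as (A or B) and C, or as A or (B and C). For start 2024, end March 2024 and injection 3 April 2024, A is false, B is true and C is true. Both readings are therefore satisfied and onset becomes 3 April. The latest possible end is 31 March, so onset follows the end by at least 3 days.

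**Neighbouring cases**, same injection date (both readings agree):

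| AE start | AE end | Result |
|---|---|---|
| 2024 | March 2024 | onset 3 April, after the end |
| 2024 | 30 March 2024 | not imputed |
| 2024 | April 2024 | onset 3 April, no contradiction |
| 2024 | missing | onset 3 April, no contradiction |
| March 2024 | March 2024 | onset 1 March, no contradiction |
| 2023 | March 2024 | not imputed |
| missing | March 2024 | pre-treatment, if the known month is compared with the injection |

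Of these, only the first row gives a contradiction. The day-missing branch cannot produce it, because its start month must be the injection month and the end cannot fall in an earlier month.

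**Calendar reach.** The screening window in the Schedule of Activities allows up to 7 days before dosing. The documents do not give injection dates. I assume 2024 for illustration, since the SAP cites a February 2024 protocol amendment and a March 2024 eCRF. With a 7-day gap, consent falls in an earlier month when injection is on days 1 to 7 of a month. January is excluded: an end in the previous month is then in December 2023, the start year cannot be 2024, and C fails. That leaves 11 × 7 = 77 dates, and 77/366 = 21%.

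**Medications.** Take start 2024, stop March 2024, and a prior-use answer that is not Yes. Appendix 4 sets the start to 3 April. For a participant still in the study, it sets the stop to 31 March. That pair falls in the empty cell of SAP Table 2. With a Yes answer, the start is 1 January and the drug is classed as prior, as it should be.

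**The case against.** The strongest objection is reach. Only SAEs, AESIs and AEs leading to withdrawal are collected. Onset of an event collected from consent is normally confined to about a week, and SAEs and AESIs are reported within 24 hours. A year-only start for such an event is implausible. Screening and dosing may fall on the same day, and acutely ill or unstable candidates are excluded. Protocol 8.2 even describes SAEs and AESIs as recorded from vaccination on Day 1, although 8.3.2 and the first footnote of the Schedule of Activities start collection at consent. All of this stands, and it limits the point to a minor one.

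A reader might infer four stronger things that the documents do not support.

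- **That the SAP declares the event treatment-emergent.** The year-only bullet gives no classification. SAP 6.4.1 speaks of AEs starting after injection, while the imputed onset equals the injection time. Counting the event follows from the purpose of the imputation. A strict reading of after would drop every AE imputed to the injection time.
- **That the whole-date-missing branch clearly gets the same event right.** It does so only if the known month of a partial end date is compared with the injection. Read strictly, its fallback could make that event treatment-emergent too. Likewise, a complete March end date stops the imputation, but the year-only branch does not then state a class.
- **That reach is much wider because a rescreened participant may keep a consent up to 28 days old.** Protocol 5.3 assigns a new participant number at each rescreening, and nothing says that an event under the earlier number is carried into the arm tables.
- **That medication summaries are equally exposed.** The fault there needs a prior-use item that is blank or contradicts the stop date. SAP 6.2.4 also defines prior use by whether the drug was taken before the injection date.

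**Conclusion.** The point holds as a wording defect in one branch of Appendix 5. Under either reading of its conditions, the rule gives an onset after the event's end when the start is year-only and a month-only end precedes the injection month in the same year. Nothing else in the SAP corrects it.

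Its practical size is very small. The 21% is a share of calendar dates, assumes a full 7-day gap and weights all 2024 dates equally. It says nothing about how often such an event would be recorded. The effect on a table, at most one event in about 100 per occurrence, rests on the inference that an onset imputed to the injection is tabulated as post-injection. The primary immunogenicity endpoint is unaffected. This is an optional improvement and not a threat to the trial's conclusions.

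**What to change.** In the year-only branch of Appendix 5, change the end-date condition so that it is met when the end date is on or after injection, is missing, or is partial with a latest possible date on or after the injection date. Add a sentence stating that an AE whose latest possible end date is before injection is a pre-treatment AE. This also settles how the whole-date-missing branch reads a partial end date.

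Events whose end date is missing, year-only in the injection year, or in the injection month keep their present conservative handling. Only events already shown by their recorded end month to precede injection change. The same wording can go into Appendix 4 for consistency.

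The cost is a short SAP edit and one date comparison in the derivation code, made before database lock and unblinding. I see no analytic downside.
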